6.4.2. Solicited systemic reactions

Definition

Solicited systemic reactions consist of nausea, vomiting, diarrhea, headache, fatigue, myalgia, arthralgia, chills, loss of appetite, malaise, or fever. They are assessed by the subject in a diary and by the investigator at specific time points stated in the protocol.

Solicited systemic reactions will be graded based on the guidance given in US Food and Drug Administration (FDA) Guidance for Industry 'Toxicity Grading Scale for Healthy Adult and Adolescent Volunteers Enrolled in Preventive Vaccine Clinical Trials'. The grades are Grade 0 (Absent), Grade 1 (Mild), Grade 2 (Moderate), Grade 3 (Severe) and Grade 4 (Potentially life threatening). Fever is graded as Mild (38.0-38.4°C), Moderate (38.5-38.9°C), Severe (39.0-40.0°C and Potentially life threatening (>40.0°C).

The solicited systemic reactions will be evaluated for the following time intervals:

- Prime immunization up to day 7 (inclusive) after prime immunization
- Boost immunization up to day 7 (inclusive) after boost immunization
- Both intervals combined

The intervals will start with the date and time of the immunization.

Clarification: The interval 'prime immunization up to day 7 after prime immunization' includes study day 1 to study day 8. This applies to the other intervals accordingly.

Analysis

Solicited systemic reactions will be analyzed in the same way as solicited local reactions (see Section 6.4.1 of the SAP).

6.4.3. Adverse events

Definition

For detailed information on adverse events see section 10.3 of the protocol.

AEs will be coded using the Version MedDRA® 23.1 including specific terms for COVID-19 to get a system organ class (SOC) and preferred term (PT) for each AE.

A TEAE is defined as any AE with an onset after the first immunization (if the AE was absent before the first immunization) or worsened after the first immunization (if the AE was present before the first immunization). AEs with an onset date more than 28 days after the last immunization will be considered as treatment emergent only if assessed as related to IMP by the investigator. AEs that cannot be determined to not be treatment emergent due to missing date or time will be defined as TEAE.

Clarification: AEs with an onset date at the date of the first immunization will only be considered as treatment emergent if the AE occurred after the first immunization.

The TEAEs will be evaluated for the following time intervals, clarifying and harmonizing the intervals defined in the protocol:

- Prime immunization up to boost immunization or day 28 (inclusive) after initial immunization (whatever comes first)
- Boost immunization up to day 28 (inclusive) after boost immunization
- All TEAEs (regardless of relationship assessment) occurring from
 - o Prime immunization up to day 28 after boost immunization (inclusive).
 - o If no boost immunization, up to 28 days (inclusive) after prime immunization All TEAEs assessed as related through visit 10.

The intervals starting or ending with an immunization, will start or end with the date and time of the immunization. TEAEs are assigned to the time intervals according to their start date and time.

Adverse events of special interest (AESI)

Enhanced respiratory disease or flu-like symptomatology not resolved after 7 days or with symptom kinetics that are inconsistent with a relationship to RNA immunization will be considered AESIs. AESIs are marked in the CRF.

Analysis

TEAEs with missing time and occurring on the day of prime immunization will be assigned to all intervals starting with the prime immunization. TEAEs with missing time and occurring on the day of the boost immunization will be assigned to all intervals including the boost immunization.

TEAEs with missing date will be assigned to all the respective intervals if it cannot be ruled out, that it belongs to a time interval.

The following TEAE types will be analyzed:

- Any TEAE
- Related TEAE
- Grade >=3 TEAE
- Related grade >= 3 TEAE

EudraCT No: 2020-003267-26

- TEAEs with dose limiting toxicity (DLT)
- Any treatment emergent serious adverse event (TESAE)
- Related TESAE
- Deaths

Overall summary of TEAEs

The number and percentage of subjects reporting at least one TEAE and the number of TEAEs will be summarized for all TEAE types defined above for each defined time interval.

The same analysis will be done for treatment emergent AESIs (TEAESIs) by time intervals.

The same analysis will be done excluding TEAEs which fulfil the following criteria:

- Are based on solicited reporting via subjects' diaries (all preferred terms included in 'BNT162-01 AEs based on solicited reporting via subjects diaries v3.0') and
- For prime or boost immunization, respectively, has a start and end date in the time period between dosing and
 - 1) the day of last diary entry (inclusive) or
 - 2) day 7 after dosing (inclusive)

whatever comes first.

TEAEs with missing start or end date will remain included.

For each defined time interval, the number and percentage of subjects reporting at least one TEAE will be summarized by PT nested within SOC for each of the following AE types:

Any TEAE, Related TEAE, Grade >=3 TEAE, Related grade >=3 TEAE, Any TESAE, Related TESAE, TEAEs with unresolved, fatal or unknown outcome, and any TEAE but excluding TEAEs which are based on solicited reporting via diaries as defined for the overall summary. If a SOC / PT is reported more than once for a subject, the subject will only be counted once for this SOC / PT. All TEAE summary tables will be sorted alphabetically by SOC and PT within SOC.

TEAE by grade

The number and percentage of subjects with TEAEs will be summarized by worst grade by PT nested within SOC by time interval. The worst grade will be counted if a TEAE is reported more than once by the same subject for this SOC / PT in one time interval.

AE listings

All AEs, AEs with DLT, AEs of subjects who discontinued early due to an AE and SAEs will be listed.

TEAE figures

The most frequent TEAEs excluding TEAEs which are based on solicited reporting via diaries will be presented graphically using a bar plot by time interval.

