# 3 OBJECTIVES AND ENDPOINTS

Objectives	Endpoints
Primary objective	
To describe the safety and tolerability profiles of BNT162b3 in healthy adults after prime/boost (P/B) immunization.	
 
Solicited local reactions at the injection site (pain, tenderness, erythema/redness, induration/swelling) recorded up to 7 d after each immunization.
 
Solicited systemic reactions (nausea, vomiting, diarrhea, headache, fatigue, myalgia, arthralgia, chills, loss of appetite, malaise, and fever) recorded up to 7 d after each immunization.
 
The proportion of subjects with at least 1 unsolicited TEAE occurring after prime immunization up to boost immunization or 28 d after prime immunization (whichever comes first) and up to 28 d after the boost immunization.
 

Secondary objectives	
To describe the immune response in healthy adults after P/B immunization measured by a functional antibody titer, e.g., VNT or an equivalent assay available by the time of trial conduct.	As compared to baseline, at 7 d and 21 d after prime immunization and at 7 d, 14 d, 21 d, 28 d, 63 d, 162 d, and 365 d after the boost immunization:  • Functional antibody responses.  • Fold increase in functional antibody titers.  • Number of subjects with seroconversion defined as a minimum of 4-fold increase of functional antibody titers.
Exploratory objectives	

Page 32 of 133 Version: 10.0 Date: 12 MAY 2021

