		Update of reactogenicity analysis: Analysis of grade >= 3 was replaced by an analysis of worst grade.	Analysis is more adequate.

Version: Final 3.0

Table of Contents

Contents

Title Pag	ge	1
Signatui	re Page	2
Version	History	3
Table of	Contents	5
1. 1.1. 1.2. 1.1.	Introduction Objectives and Endpoints Study Design Schedule of Visits and Procedures	7
2.	Statistical Hypotheses	.12
3. 3.1.	Interim Analyses Data Monitoring Committee (DMC)	
4.	Sample Size Determination	.14
5. 5.1. 5.2. 5.3.	Analysis Sets and Subgroups Analysis Sets Protocol Deviations Subgroups	.15
6. 6.1.	Statistical Analyses	.17
6.1.1. 6.1.2. 6.1.3.	Tables and Listings Definitions and Derivations	.18
6.2. 6.3. 6.3.1.	Subject Dispositions Baseline Characteristics Demographics	.19
6.3.2. 6.3.3. 6.4.	Concomitant Medication. Medical History Primary Analyses	.20
6.4.1. 6.4.2.	Solicited local reactions	.21
6.4.3. 6.5. 6.5.1.	Adverse events Secondary Analyses Functional antibody response	.25
6.5.2. 6.5.3.	Functional antibody titers fold increase	.26
6.6. 6.7. 6.7.1.	Exploratory Analyses Further Safety Analyses Compliance	.26
6.7.1. 6.7.2. 6.7.3.	Laboratory Assessments	.27

8.	References	33
7.3.	Appendix 3: Reporting Conventions	32
7.2.	Appendix 2: List of Abbreviations	30
7.1.	Appendix 1: Changes to Protocol-Planned Analyses	30
7.	Supporting Documentation	30
6.7.5.	Further Safety data	29
6.7.4.	ECG	

1. Introduction

EudraCT No: 2020-003267-26

This document presents the statistical analysis plan (SAP) for BNT162-04, a dose-escalation phase I/II study in healthy subjects. The results of this study might be included in a regulatory submission.

This SAP describes the detailed procedures for the planned statistical analyses for protocol version 10.0, dated 12 MAY 2021 (hereinafter referred to as "the protocol"). Changes from the protocol are documented in Section 7.1 Appendix 1.

The study consists of two parts, Part A and B. All analyses of Part A except for exploratory endpoints are described in this SAP including the analysis of CRF and laboratory data. The exploratory analyses will be described in a separate biomarker SAP developed by BioNTech. Due to changes in the overall clinical development plan, Part B will no longer be conducted.

[figure not shown]
The statistical analyses described in this document will be conducted by Staburo GmbH using SAS® software version 9.4 or higher.

This study will evaluate safety, adverse events and immunogenicity assessments data.

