6.1. General Considerations

The following described statistical analyses only refer to Part A of the study.

No formal statistical testing will be done.

Unless otherwise specified, analyses will be based on data pooled across all study sites.

Data assessed after the vaccination with a non-trial vaccine will be excluded from all statistical analyses.

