6.2. Subject Dispositions

For the SCR, a listing of subjects having failed screening will be presented.

Subject disposition will be listed with date of informed consent, date of screening, date of immunization and date of study completion/discontinuation.

The number and percentage of subjects in the analysis sets will be summarized by group (i.e. by cohort) and cohort-total for the subjects in the SAF.

For the SAF, number and percentage of subjects having prematurely discontinued the study with a summary of the primary reason (e.g., adverse events, death, withdrawal by subject, lost to follow-up), of subjects who completed the end of treatment phase (merged from End of Trial variable and End of Treatment variable (each subject has only one data entry)) and who completed the follow-up phase will be presented by group (i.e. by cohort) and cohort-total.

Subjects having prematurely discontinued will be listed with date and reason for premature discontinuation.

Subjects in the SCR but excluded from SAF, subjects in SAF but excluded from SAFB/ IMM/ IMMPP will be listed with reason for exclusion.

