6.7.5. Further Safety data

Physical examination, drugs of abuse, alcohol use, viral screening and the SARS-CoV-2 testing will be listed.

7. Supporting Documentation

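### SAEs and proven COVID-19 cases that start more than 28 days after the last dose and are judged unrelated enter no AE summary table

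*SAP*

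**What the plan says.** - **Definition (SAP 6.4.3; same rule in protocol 10.3.1).** "AEs with an onset date more than 28 days after the last immunization will be considered as treatment emergent only if assessed as related". An AE whose missing date or time leaves the matter open defaults to TEAE, so the point concerns events with a known late onset.
- **Intervals (SAP 6.4.3).** The intervals that ignore causality end on day 28 after the last dose. The only later one is "All TEAEs assessed as related through visit 10". SAP 7.1 confirms that late events enter by that route.
- **Tables (SAP 6.4.3).** The overall, SOC/PT, worst-grade and special-interest summaries and the figures are all of TEAEs or treatment-emergent SAEs. Deaths are named as one of the TEAE types.
- **Listings (SAP 6.4.3).** "All AEs, AEs with DLT, AEs of subjects who discontinued early due to an AE and SAEs will be listed". SAP 6.1.1 puts cohort in the listings and sorts by it first.
- **Disposition (SAP 6.2).** Early discontinuations are counted by primary reason, with AEs and death among the examples.
- **Truncation (SAP 6.1).** "Data assessed after the vaccination with a non-trial vaccine will be excluded from all statistical analyses".
- **Scope (SAP 1).** "All analyses of Part A except for exploratory endpoints are described in this SAP including the analysis of CRF and laboratory data". Exploratory work goes to a separate biomarker SAP.
- **Collection.** Protocol 10.3.1.9 and footnote j of the Schedule of Activities (SoA) require every proven COVID-19 case, mild ones included, to be recorded up to the last follow-up visit whatever the causality. Moderate and severe cases are SAEs and get a narrative. Footnote j also asks for any SAE at Visits 8, 9 and 10.

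**The concern.** The protocol takes trouble to gather late COVID-19 cases irrespective of causality, and one stated aim of Amendment 02 was to avoid under-reporting of mild ones. Protocol 2.3.1 adds that enhanced disease cannot be ruled out. The SAP then makes tabulation depend on causality: late related events are counted and late unrelated ones are not. COVID-19 is a community infection, so I would expect many cases to be judged unrelated; that is my inference, not a statement in the documents.

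This is an open-label trial whose primary objective is to describe safety, so counts by cohort are its main product. A reader of the SAE tables could take them as all-cause for the whole trial. For most of follow-up they would hold related events only.

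**Working it through.** **The plan's own figure.** SAP 4 gives an 85.8% chance of seeing a TEAE of 15% incidence at least once in 12 subjects. 1 − 0.85^12 = 0.858, so it reproduces. The point does not depend on it.

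**Step 1: apply the SAP 6.4.3 rules.**

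| Onset after last dose | Judged related | Judged unrelated |
|---|---|---|
| 28 d | TEAE; all-cause and related intervals | TEAE; all-cause interval |
| 29, 63, 162 or 365 d | TEAE; related interval only | Not a TEAE; no interval, no AE table |

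**Step 2: length of the gap.** Inputs from the SoA: prime Day 1, boost Day 22±2, Visit 7 Day 50, Visit 8 Day 85, Visit 9 Day 184, Visit 10 Day 387±14.

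- Boosted: cut-off 22 + 28 = Day 50. Gap 387 − 50 = 337 d. Post-boost follow-up 387 − 22 = 365 d. 337/365 = 92.3%.
- With visit windows: shortest 373 − (24 + 28) = 321 d; longest 401 − (20 + 28) = 353 d.
- No boost: cut-off 1 + 28 = Day 29. (387 − 29)/(387 − 1) = 358/386 = 92.7%.

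**Step 3: effect of SAP 6.1.** The dates of non-trial vaccination are assumptions.

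- At Visit 8: (85 − 50)/(85 − 22) = 35/63 = 55.6%.
- At Visit 9: (184 − 50)/(184 − 22) = 134/162 = 82.7%.

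**Step 4: which late SAEs were to be collected.** For proven COVID-19 the rule is clear. For other SAEs the protocol passages differ:

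| Protocol passage | Visit 7 to Visit 9 | Visit 9 to Visit 10 |
|---|---|---|
| SoA footnote j | Any SAE | Any SAE |
| 8.3.1 | Can be read as any SAE or as related SAEs only | No duty to seek events actively |
| 10.3.1.7 | Safety monitored | Monitoring ends about 6 months after the last dose |
| 10.3.1.10 | Any SAE within the observation period | Related only, once that period has ended |

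The 337 days split into 184 − 50 = 134 d (36.7% of 365), where footnote j and one reading of 8.3.1 call for any SAE, and 387 − 184 = 203 d (55.6%), where only footnote j does.

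**The case against.** The strongest reply is that the SAP does what the protocol asks. Protocol 9.4.2 plans TEAE-based summaries, 10.3.1 sets the 28-day rule, and no primary or secondary objective needs all-cause counts to Visit 10. The cut-off also has a rationale: all AEs are collected to Visit 7, which for boosted subjects is day 28 after boost. This stands, and it is why the TEAE definition should stay. The match fails for subjects without a boost: their tables stop at Day 29 although full collection runs to Day 50, 21 days later. Protocol 9.4.2 also leaves room for further AE analyses in the SAP.

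Three stronger readings are tempting, and the documents do not support them.

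- *Late unrelated events go unreported.* They do not. With 12 subjects per cohort and listings sorted by cohort, a reader can count them by hand, and moderate or severe COVID-19 also gets a narrative. Completeness of the listings is nevertheless not assured: SAP 6.1 does not say whether its exclusion reaches them, and SAE collection is itself in conflict.
- *The plan would hide enhanced disease.* An event with a reasonable possibility of vaccine causation is related under protocol 10.3.1.7 and is tabulated through Visit 10. Without a control group, all-cause counts could not identify enhanced disease anyway.
- *No analysis plan tabulates COVID-19 cases.* This cannot be verified. Amendment 02 gives, as the reason for the reporting changes, study of how protection relates to immunology. That suggests exploratory use, and the biomarker SAP is not among the documents.

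**Conclusion.** The gap is real but limited to presentation. An SAE or proven COVID-19 case with known onset more than 28 d after the last dose, judged unrelated, is in no AE summary table. The period is up to 337 of 365 scheduled post-boost days (92%), or 358 of 386 days after prime without a boost (93%).

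These figures assume scheduled visit days, follow-up to Visit 10 and no non-trial vaccine; SAP 6.1 shortens the period where one was given. They measure follow-up time, not events: the documents give no event rate, so the number of events affected is unknown. For SAEs other than COVID-19, what can be tabulated also depends on which collection rule the sites followed.

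The primary AE endpoint, which runs "up to 28 d after the boost immunization", is untouched. I rate this as a cheap improvement that should be made, not as a flaw in the main analysis.

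**What to change.** Keep the TEAE definition and add to SAP 6.4.3 one summary by cohort and in total, giving subjects and events, from prime through Visit 10 whatever the causality, of:

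- all collected SAEs, including fatal ones;
- proven COVID-19 cases by severity, flagging those that are also SAEs so that they are not counted twice.

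State whether the SAP 6.1 exclusion applies to this summary and to the listings. If it does, give the follow-up time each cohort contributes. If the biomarker SAP already tabulates COVID-19 cases, a cross-reference is enough for that part.

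Separately, SoA footnote j and protocol 8.3.1, 10.3.1.7 and 10.3.1.10 must be reconciled on SAE collection after Visit 7, above all from Visit 9 to Visit 10. The rule actually applied should stand beside any SAE count for that period. Follow-up was due to be over before the SAP date: vaccinations were complete by 12 March 2021, the longest boost-to-Visit 10 gap within the windows is 401 − 20 = 381 d, which ends on 28 March 2022, and SAP v3.0 is dated 27 April 2022. What remains is to document the rule.

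Cost: one or two descriptive tables from data already held, a follow-up-time calculation per cohort if SAP 6.1 applies, and one explanatory note. No new visits or data.

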# 8.3.1 Time period and frequency for collecting AE and SAE information

All AEs and SAEs will be collected from the date of subject consent until Visit 7; after Visit 7 (at Visits 8 and 9), only IMP-related AEs and SAEs will be collected.

All SAEs (initial and follow-up reports) will be recorded and reported to the sponsor or designee within 24 h after becoming aware of the event, as indicated in Section 10.3.1.10.

Investigators are not obligated to actively seek AEs or SAEs between Visit 9 and Visit 10 and after conclusion of the trial participation. However, if the investigator learns of any SAE, including a death, at any time after a trial subject has been discharged from the trial, and he/she considers the event to be reasonably related to the IMP administration or trial participation, the investigator must promptly notify the sponsor.

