7.1. Appendix 1: Changes to Protocol-Planned Analyses

•

- TEAEs after 28 days after last dose are included in the overall time interval ('All TEAEs assessed as related through visit 10')
- In protocol section 9.4.2 it is stated "For each injection, the number and percentage of subjects reporting at least one local reaction or systemic reaction (i.e., solicited data collected using subject diaries) will be summarized for each of the following types using the Safety Set:
 - · Any local reactions or systemic reactions
 - Grade ≥3 local reactions or systemic reactions".

However, for each injection, the number and percentage of subjects reporting at least one local reaction or systemic reaction (i.e., solicited data collected using subject diaries) will be summarized for any local or systemic reactions as well as worst type of local or systemic reaction. No summary of grade ≥3 local reactions or systemic reactions will be presented.

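### An AE present before the prime dose that worsens afterwards is a TEAE by definition, but the start-date rule in SAP 6.4.3 keeps it out of the prime and boost windows

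*SAP*

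**What the plan says.** **Definition.** Under SAP 6.4.3 an AE is treatment emergent if it begins after the first immunization, or if it "worsened after the first immunization (if the AE was present before the first immunization"). Protocol 10.3.1 has the same second limb.

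**Placement.** SAP 6.4.3: "TEAEs are assigned to the time intervals according to their start date and time". On the bounds: "The intervals starting or ending with an immunization, will start or end with the date and time of the immunization". There is a prime interval, a boost interval and a combined interval running to 28 days after the boost (or after the prime dose, if no boost is given). Next to the combined interval stands one further component, "All TEAEs assessed as related through visit 10". SAP Appendix 1 explains it: "TEAEs after 28 days after last dose are included in the overall time interval".

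**Output.** Counts in the overall summary "will be summarized for all TEAE types defined above for each defined time interval". For the coded tables: "For each defined time interval, the number and percentage of subjects reporting at least one TEAE will be summarized by PT nested within SOC". The worst-grade table and the bar plot are also by interval. All AEs are listed, whatever their interval.

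**Data collection.** Protocol 8.3.1: "All AEs and SAEs will be collected from the date of subject consent until Visit 7". The schedule of activities lets screening start at Day -30, and Protocol 10.3.1 treats events between consent and dosing as AEs.

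**The concern.** The definition turns on when an AE worsened; the placement rule looks only at when it started. For an AE already present before the prime dose these are different dates, and the one the rule uses lies before every dated interval opens. Since all TEAE tables are built from intervals, a programmer following the text literally would classify such an event as a TEAE and then have no dated interval to put it in.

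The third primary endpoint is the proportion of subjects with at least one unsolicited TEAE in the post-prime and post-boost windows. The events at risk are ones the plan itself defines as treatment emergent, and leaving them out can only lower that proportion.

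**Working it through.** **Inputs.** The TEAE definition, placement rule, interval bounds and table list come from SAP 6.4.3. The 12 subjects per cohort come from SAP section 4. The boost falls 21 days after the prime dose. The AE below is an assumed illustration: onset 5 days before the prime dose, worsening either 2 or 25 days after it.

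**The plan's only figure nearby.** SAP section 4 gives 85.8% as the chance of seeing a TEAE of 15% incidence at least once in 12 subjects. 1 − 0.85^12 = 0.8578, so it reproduces. It does not depend on the point made here.

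**Step 1: interval bounds.** Count days from the prime dose (prime = 0, boost = 21). The prime interval ends at the earlier of 21 and 28, so it is 0 to 21. The boost interval is 21 to 21 + 28 = 49. The combined interval is 0 to 49. The related component ends at Visit 10 and has no stated start.

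**Step 2: place the same AE by each date.**

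| Date used | Prime (0–21) | Boost (21–49) | Combined (0–49) | Related through Visit 10 |
|---|---|---|---|---|
| Onset, day −5 (current rule) | no | no | no | only if related |
| Worsening, day +2 | yes | no | yes | only if related |
| Worsening, day +25 | no | yes | yes | only if related |

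Under the current rule an unrelated event of this kind sits in no interval. A related one sits only in the last column.

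**Step 3: do the missing-date rules rescue it?** No. They apply when a date or time is missing, and here the pre-dose start is known. The result is odd: a TEAE with no date goes into every interval that cannot be excluded, while one known to have worsened after dosing goes into none of the three dated intervals.

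**Step 4: can such a record arise?** Yes, if an AE begins after consent and before the prime dose and is kept as one entry. Protocol 10.3.1.7 makes the recorded start the time of onset. Protocol 8.3.3 sends new information on an AE to the CRF entry already completed. Nothing tells the site to open a second entry when such an AE worsens.

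**Step 5: size.** In a cohort of 12, one missed subject is 1/12 = 8.3 percentage points and two are 2/12 = 16.7. These are upper bounds. The endpoint counts subjects, so the proportion moves only if the missed subject has no other TEAE in that window.

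**The case against.** The case against is strong on scope.

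- **Related events are not lost altogether.** The related component has no stated lower bound, and Appendix 1 places it in the overall interval. A related worsened TEAE, including a serious or Grade 3 one, is therefore counted there. This stands, although such an event still misses the two windows that define the primary endpoint.
- **Worsening can be its own AE.** Protocol 10.3.1.1 lets the investigator report worsening of a pre-existing condition as an AE, and the outcome rules in 10.3.1.7 refer to AEs documented in that way. Such a record starts after dosing and is placed normally. This stands for pre-existing conditions. For AEs that began after consent the documents are silent, and the CRF completion manual is not available here.
- **Few events are likely.** Subjects are healthy, and acute illness within 72 hours before the first dose is generally excluded. Collecting AEs from consent does not show that any pre-dose AE occurred. All AEs are listed, and no hypothesis is tested. All of this stands.

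A reader might infer that every TEAE of the worsened kind vanishes from every table. The first two points show that the documents do not support this.

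A reader might also infer that the rule wrongly charges the prime dose with an AE that starts after it and worsens after the boost. That is a choice of convention. The TEAE definition is anchored on the first immunization, placement by onset fits the endpoint's wording, and the combined interval keeps the event and its grade. It does not make the vaccine as a whole look better tolerated.

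**Conclusion.** The point holds in a narrow form. The definition and the placement rule in SAP 6.4.3 conflict for an AE that began between consent and the prime dose, stays one record with its pre-dose start, and worsens after dosing. The prime and boost windows of the third primary endpoint miss it. If unrelated, it enters no TEAE table; if related, only the component running through Visit 10 counts it. The listing of all AEs keeps it visible in either case.

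The number affected cannot be derived from the documents. It is probably small, given how short the pre-dose period is and how healthy the subjects are. The effect is at most 8.3 points per missed subject in a cohort of 12, under the condition in the working. The conclusion assumes that the start-date rule is applied as written and that the site updates the existing entry when the AE worsens. This is a stated rule that gives the wrong result for one class of event, so it should be corrected. Priority is low to moderate; the likely count does not support treating it as a must-fix.

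**What to change.** In SAP 6.4.3, directly after the sentence that places TEAEs by start date and time, add:

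> A TEAE that was present before the first immunization and qualifies by worsening is assigned by the date and time of worsening; if that date is not recorded, it is assigned to every interval that cannot be ruled out, as for missing dates.

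The sentence should be limited to AEs present before the first immunization. AEs that start after the prime dose stay assigned by start date. A wider rule would move an AE that began after the prime dose and worsened after the boost out of the prime window, where it belongs. It would also help to state where the component for related TEAEs through Visit 10 begins.

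The cost is one sentence and a rerun of the AE tables and bar plot, with no new data collection. The downside is that Protocol 10.3.1.7 names start, end and intensity for the CRF but no date of worsening. The fallback may therefore be needed, and one event may then be counted in both the prime and the boost interval. A footnote giving the number of TEAEs placed by the fallback would make this visible.
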